### 11.10.3 Resource utilization

We will collect data on direct costs (i.e., costs of visits to healthcare providers plus cost of medications) and indirect costs (e.g., travel costs). For direct costs, we will ask parents/legal guardians about the number and type of encounters with healthcare providers since enrollment. Similarly the types and duration of medication used will be ascertained. For indirect costs, we will ask parents/legal guardians about travel expenses, alternate child care expenses (for the patient and/or siblings), as well as time costs (e.g., for missed work). These assessments will be conducted at the time of the end-of-study follow-up visit.

## 11.11 Sample Size Justification

To estimate the sample size for this trial, we used estimates of within-subject correlation and grand variance from our preliminary data of children diagnosed with acute sinusitis. Because two simultaneous tests for interactions are being conducted, we used a two-sided significance level of 0.025 (50:50 split of the overall significance level of 0.05 for Bonferroni adjustment).

Assuming an  $\alpha$  of 0.025 (two-sided test), 344 evaluable children per treatment group will provide statistical power of 80% to detect an interaction effect size of 2.5 points in the mean symptom score (as measured by the PRSS) over the 10-day period assuming, as per results presented in Leon and Heo, that the required sample size to detect an interaction between treatment group and a subgroup would be four times that of a main effect of the same magnitude for a repeated measures outcome under a 2x2 factorial design.

Even though we have calculated the sample size using the simple Bonferroni procedure, for the final analysis we will use a modified Bonferroni procedure for multiple testing, which is not as conservative for highly correlated test statistics. Under the Simes' procedure, the null hypothesis associated with the smallest p-value will be rejected if the p-value is smaller than or equal to  $\alpha / 2$  and one associated with the second smallest p-value will be rejected if the p-value is smaller than or equal to  $\alpha / 2$ . Here  $\alpha / 2$  is the appropriate significance level for the interim or definitive analysis. Specifically, the (ordered) observed p-values will be compared using 0.0025 and 0.005 for the interim analysis and using 0.024 and 0.048 for the definitive analysis.

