#### 2.1.3 Preliminary studies

In preparation for this trial, we prospectively enrolled 276 consecutive children aged 2 to 12 years with persistent or worsening presentations of acute sinusitis from 6 outpatient clinics in Pittsburgh (NIH R21AI076677, [name], PI). The aims of this observational study were to (1) develop and validate a symptom severity scale; (2) identify important prognostic factors that could be used to define subgroups in the present study; and (3) determine signs and symptoms associated with likely bacterial sinusitis, which could then be used to define subgroups for the present study. We screened 2023 children with URI symptoms for eligibility. A total of 355 (18%)

children met clinical criteria for the diagnosis of persistent or worsening presentations of acute sinusitis, and parents/legal guardians of 276 children agreed to enroll their children in our observational study. The mean age (standard deviation) of children enrolled was 6.4 (2.9) years. Almost all children (n=267) had sinus radiographs performed on the day of diagnosis and most (n=204) had a nasopharyngeal swab collected for bacterial culture (for reasons explained below). A large majority of children received antimicrobial therapy (n=227). Seventy six percent of children had abnormal sinus radiographs and 49% had pathogens (*S. pneumoniae*, *H. influenzae*, or *M. catarrhalis*) isolated from their nasopharynx.

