After obtaining written informed consent from the parent/legal guardian, we will gather information on the following potential predictors and confounders: demographic characteristics, risk factors (day care attendance, previous systemic antimicrobial use, exposure to household cigarette smoke), symptoms (type and duration, including some symptoms not included on the PRSS), past medical history (sinusitis, AOM, allergic rhinitis, asthma, pneumococcal vaccination), temperature and weight measurement (if not already taken for clinical care), and concomitant medications. Temperature will be measured using appropriate method according to the child's age and parental preference (oral, rectal, axially, temporal, or tympanic). We will assess the nose and throat for facial tenderness and swelling. A nasopharyngeal swab will be obtained, when possible, and placed in transport media and sent to the Microbiology Laboratory-CHP for processing. In the event a nasopharyngeal swab is unable to be obtained, the study team will attempt to obtain a mid-turbinate nasal swab. When possible, the first dose of the study product will be given at the time of enrollment following randomization and monitoring of adverse events will begin. This will reduce variability due to delay in the initiation of therapy. We will ask parents/legal guardians to refrain from administering intranasal medications (e.g., corticosteroids, decongestants), and systemic medications containing antihistamines, decongestants or corticosteroids to their child for the duration of the study. We will assess whether the nasal discharge is colored. In our preliminary study (n=276), we showed that asking parents/legal guardians directly about the color of the nasal discharge (In the last 24 hours, was your child's nasal discharge (mucus) yellow or green?) yielded information that was predictive of both the bacteria cultured from the nasopharynx (p=.006) and the findings of sinus radiographs (p=.003). Parental/legal guardian report of "white" discharge or physician examination of the anterior nares or nasal turbinates for colored discharge was not similarly informative. As an additional method of assessing color, we will utilize a color chart (with 4 colors: green, yellow, white, clear) and ask parents/legal guardians to identify the color that most closely resembles their child's nasal discharge. Nevertheless, based on our strong preliminary data, and based on the fact that the assessment of nasal discharge using a color chart is unlikely to be practical in a busy clinical practice, asking parents/legal guardians whether their

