## 11.6 Statistical Analyses

### 11.6.1 General Considerations

Study data will be monitored on an ongoing basis by the Data Management and Statistical Unit in the Division of General Academic Pediatrics at the Children's Hospital of Pittsburgh. Final cleaning and editing of the study database will be carried out after the last patient completes follow-up. Unblinding of treatment assignments will not be performed until the study data are cleaned, queries resolved, and database lock achieved. All changes to the study database will be documented. A permanent archive of the database will be maintained by the DMSU.

A 2x2 factorial design, adjusted for multiple testing, will be used to detect interactions for the longitudinal outcome, where Factor A will be antibiotic-treated vs. placebo and Factor B will be either colored nasal discharge (yellow or green vs. clear) or nasopharyngeal colonization (positive vs. negative).

All statistical tests will be two-tailed and conducted at global significance level of 0.05. For the primary efficacy analysis, the significance level for the final analysis will take into account the interim analysis. Sites with few children randomized may be pooled. Pooling of study sites will occur prior to unblinding. All programs used in the statistical analysis will be documented, tested, and archived. Archiving of statistical analyses at the DMSU includes the original written specifications for the analyses, any subsequent modifications, the computer program file, and the log, list and other output files produced by the program. The DMSU will use the most current version of SAS®.

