### 11.6.2 Interim Analysis

Interim analysis will occur after 344 children have completed this trial. Type I error will be controlled using the method of Fleming, Harrington and O'Brien and testing will be conducted at significance levels of 0.005 and 0.048 at the interim and final analyses, respectively. If at least one of the tests for interaction is significant (i.e., if there is unequivocal evidence of treatment effect heterogeneity), the DSMB may consider recommending stopping this trial early.

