### **11.7 Efficacy Analyses**

#### **11.7.1 Primary Efficacy Analysis of the Primary Efficacy Endpoint**

We present compelling preliminary data and extensive literature suggesting that the effect of antimicrobial therapy is likely to differ in certain subgroups of children with acute sinusitis. Accordingly, the primary efficacy analysis will assess the heterogeneity of treatment effect in subpopulations defined by presence of nasopharyngeal colonization and by the presence of colored nasal discharge (i.e., to test for interaction between treatment and subgroup effects).

Interactions between treatment group and each subgrouping variable will be tested simultaneously. A Generalized Estimating Equations (GEE) model will be fit by including treatment by subpopulation interaction terms (adjusted for the baseline PRSS score) using the ITT dataset (see Section 6.8 for detailed multiple testing procedure). The regression analysis will be adjusted for clinical site as a potential confounding factor.

Assumptions required for the validity of GEE will be assessed. These will include (i) the marginal mean of the response depends on a link function, (ii) the marginal variance depends on the marginal mean, and (iii) the correlation within subject depends on the marginal mean and other parameters. Therefore an appropriate link function will be chosen for the primary outcome and the goodness of fit of the model will be assessed.

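### The primary multiplicity rule has no step-up link: with final p-values of 0.030 and 0.040 it rejects the larger and retains the smaller

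*Combined protocol and SAP*

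**What the plan says.** Section 11.7.1 makes two interaction tests primary: "Interactions between treatment group and each subgrouping variable will be tested simultaneously". For the procedure it tells the reader to "see Section 6.8 for detailed multiple testing procedure". Section 6 ends at 6.6, so that pointer leads nowhere.

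The rule itself is in Section 11.11, under the sample size. It names a modified Bonferroni procedure and cites Simes. One sentence gives a criterion for the smallest p-value and then a separate one for the other: "one associated with the second smallest p-value will be rejected if the p-value is smaller than or equal to" its own threshold. The operative numbers follow: "the (ordered) observed p-values will be compared using 0.0025 and 0.005 for the interim analysis and using 0.024 and 0.048" for the final analysis. They are built on Section 11.6.2, where "testing will be conducted at significance levels of 0.005 and 0.048 at the interim and final analyses, respectively", and on Section 11.6.1: "All statistical tests will be two-tailed and conducted at global significance level of 0.05".

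No sentence in these sections connects the two decisions.

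**The concern.** A test on ordered p-values needs a direction. In a step-up rule, rejecting the hypothesis with the larger p-value carries the smaller with it. In a step-down rule, the larger is examined only after the smaller has been rejected. Section 11.11 states neither. With two free-standing cut-offs, the smaller p-value faces the stricter one and gets no credit when the larger passes. If both lie above 0.024 and at or below 0.048, the hypothesis with the weaker evidence is rejected and the one with the stronger evidence is retained.

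This rule decides both primary hypotheses. Followed literally, it can discard a rejection to which the trial is entitled and report a pair of results that would be hard to defend. An analyst who notices the problem after unblinding would have to choose between rejecting one, both or neither, and that choice should be fixed beforehand.

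**Working it through.** **1. The plan's cut-offs.** The Simes critical values for two hypotheses are i × α / 2, with i = 1, 2. At α = 0.048 they are 0.024 and 0.048; at α = 0.005 they are 0.0025 and 0.005. Both pairs reproduce Section 11.11 exactly. The levels 0.005 and 0.048 at half the information give an overall two-sided error of 0.0499 for one hypothesis, consistent with 0.05. The numbers are sound; the fault lies in how they are applied.

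**2. The rules on example p-values.**

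| p-values | As written | Step-up (Hochberg) | Step-down (Holm) |
|---|---|---|---|
| 0.020, 0.040 | both | both | both |
| 0.030, 0.060 | neither | neither | neither |
| 0.030, 0.040 | only the 0.040 | both | neither |
| 0.003, 0.004 (interim) | only the 0.004 | both | neither |

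The written and step-up rules differ only when both p-values lie in (0.024, 0.048], or in (0.0025, 0.005] at the interim.

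**3. Which rule the named procedure implies.** Use the Simes test for the joint null and require each hypothesis to survive its own test at 0.048 (closed testing). The joint null is rejected if the smaller p-value is at most 0.024 or the larger is at most 0.048. If the larger is at most 0.048, the joint null and both single nulls fall, so both are rejected. Otherwise only the smaller can be rejected, and only if it is at most 0.024. That is the Hochberg rule with the plan's own cut-offs.

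**4. Inputs for the frequency.**
- Effect size. 80% power at two-sided 0.025 (Section 11.11) gives a mean z of 2.241 + 0.842 = 3.083.
- Correlation between the tests. The documents do not give it, so it is an assumption. Section 7.2 reports parent-reported discharge colour as "predictive of both the bacteria cultured from the nasopharynx (p=.006"), and Section 2.1.3 says that "most (n=204) had a nasopharyngeal swab collected for bacterial culture". Taking n = 204, phi = z/√n = 2.75/14.28 = 0.19. This suggests about +0.2 if the interactions are fitted in separate models and about -0.2 if in one model. Wider values are shown.

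**5. Probability of the reversal at the final cut-offs** (bivariate normal, both p-values in (0.024, 0.048]):

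| Mean z of the two tests | ρ = -0.2 | 0 | 0.2 | 0.5 | 0.9 |
|---|---|---|---|---|---|
| 0, 0 | 0.07% | 0.06% | 0.07% | 0.15% | 0.53% |
| 3.083, 0 | 0.17% | 0.17% | 0.17% | 0.16% | 0.04% |
| 2.1, 0 | 0.25% | 0.27% | 0.25% | 0.15% | 0.00% |
| 1.0, 1.0 | 0.29% | 0.37% | 0.45% | 0.63% | 1.45% |
| 1.5, 1.5 | 0.79% | 0.85% | 0.92% | 1.11% | 2.27% |
| 2.1, 2.1 | 1.26% | 1.24% | 1.26% | 1.43% | 2.76% |
| 3.083, 3.083 | 0.40% | 0.49% | 0.58% | 0.77% | 1.69% |

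For independent tests under the global null the figure is simply 0.024² = 0.0006. At the interim cut-offs, with both effects at design and half the information, it is 0.39%, 0.43% and 0.48% for ρ = -0.2, 0 and 0.2.

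**6. Both looks together** (simulation, assuming the trial stops after any interim rejection):
- Both effects at design: the chance of rejecting both rises from 47.8% to 48.6% (ρ = -0.2), or from 53.3% to 54.4% (ρ = 0.2), when the step-up link is added.
- The chance of rejecting at least one is identical under the two rules, because every added rejection occurs in a trial that already had one.
- Family-wise error under the global null is about 5.0% under both rules for ρ from -0.2 to 0.2.
- With one true interaction at design, the false rejection rate of the other moves from about 3.55% to 3.63% (ρ = ±0.2), still below 5%.

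**The case against.** The strongest reply is that the plan names Simes and speaks of ordered p-values, so a competent analyst would supply the link and would never report 0.040 as significant beside a non-significant 0.030. The text could also be read as step-down, in the order in which the criteria are listed; the defect would then be an unstated direction, not a reversal. The step-down reading does not fit the named procedure: step 3 shows that closing the Simes test gives the step-up rule. The reply about the competent analyst has some force in practice. But the protocol chose to write the rule out, and naming a method does not replace an explicit decision rule for the primary hypotheses. That several readings can be argued is a further reason to fix the wording.

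A second reply is that the formula in Section 11.11 shows α/2 for both thresholds, and with 0.024 for both no reversal can occur. That may be a symbol lost when the PDF was read. The sentence that follows gives 0.024 and 0.048 explicitly, so those values govern. If α/2 is truly printed twice, the formula contradicts the numbers.

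A third reply is that separate analysis specifications may exist, since Sections 9.6 and 11.6.1 allude to them. They are not part of this document and cannot be assumed to close the gap.

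What stands is the point about size: the event is rare, error control is intact, and the interim condition in Section 11.6.2, which needs only one significant interaction, is unaffected.

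**Conclusion.** The rule is wrong as written. When both p-values fall between the two cut-offs it retains the hypothesis with the stronger evidence, and nothing else in the document corrects it. Rejecting at 0.040 is valid; the error is not rejecting at 0.030 with it.

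The effect is small. Under the assumed correlations of -0.2 to 0.2, it concerns roughly 0.3% to 1.3% of final analyses when both interactions are real (mean z from 1.0 to 3.083), and less otherwise. Over both looks at the design effect it costs about 0.8 to 1.1 percentage points of the chance of rejecting both. These sizes rest on an assumed test correlation, normal test statistics, an interim at half the information and stopping after any interim rejection. The reversal itself rests only on the stated cut-offs. It should be corrected because it is the primary decision rule and the correction is nearly free.

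**What to change.** Replace the rule in Section 11.11 with an explicit step-up statement:

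- **Final analysis:** if the larger p-value is at most 0.048, reject both interaction hypotheses; otherwise reject only the one with the smaller p-value, provided that it is at most 0.024.
- **Interim analysis:** the same, with 0.005 and 0.0025.

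Change the pointer in Section 11.7.1 from Section 6.8 to Section 11.11. Compare the α/2 expressions in Section 11.11 with the source file and make them agree with the stated numbers.

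The cost is one sentence and one cross-reference. Cut-offs and sample size stay the same, no power is lost, and family-wise error stays within the range shown above. The wording should be settled before any unblinded interim look.

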## **12 SOURCE DOCUMENTS AND ACCESS TO SOURCE DATA/DOCUMENTS**

Each participating clinical study site will maintain appropriate medical and research records for this trial, in compliance with ICH E6, Section 4.9 and regulatory and institutional requirements for the protection of confidentiality of subjects. Each participating clinical study site will permit authorized representatives of DMID, University of Pittsburgh or its designee, and appropriate regulatory and monitoring agencies to examine (and when required by applicable law, to copy) clinical trial records for the purposes of quality assurance reviews, audits, monitoring and evaluation of the study safety and progress. These representatives will be permitted access to all source data. All sites use certified, comprehensive Electronic Health Record (EHR) systems requiring privacy and security compliance and HIPAA and institutional policies addressing unauthorized access to the EHR systems; these policies preclude external representatives listed in this protocol from accessing the EHR. However, paper copies of the respective EHR system documentation may be provided to the monitors for review.

Web-based electronic case report forms (eCRFs) will be the source documents for data collected during the study visits. These forms will be accessible from all study sites using a secure website managed by the DMSU. The data system includes features such as password protection, automatic time/date stamps, and automatic range checks that will identify data that appear inconsistent, incomplete or inaccurate. Electronic forms facilitate the generation of clean datasets by guiding investigators through the data collection process in such a manner as to display only questions and screens that are appropriate for the particular subject, thus minimizing the possibility of incorrect entries. An electronic audit trail of all changes will be maintained by the system (i.e., by recording old vs new value, date, time and reason for change). The database also performs an important tracking function by monitoring such parameters as missed follow-up appointments to ensure that the required data collection instruments are administered within the time constraints dictated by the study protocol. All files will be backed-up daily and archived weekly.

Additional source documents include the patient's medical record (i.e., for children who are prescribed another antibiotic while on study product), and laboratory reports (entered into the eCRF by the staff at the Microbiology Laboratory at CHP).

## **13 QUALITY CONTROL AND QUALITY ASSURANCE**

Following a written DMID-accepted site quality management plan, the participating clinical study sites are responsible for conducting routine quality assurance (QA) and quality control (QC) activities to internally monitor study progress and protocol compliance.

The principal investigators will provide direct access to all participating clinical study sites, source data/documents, and reports for the purpose of monitoring and auditing by DMID and University of Pittsburgh or its designee, and inspection by local and regulatory and authorities.

The principal investigator will ensure all study personnel are appropriately trained and applicable documentation is maintained on site.

The DMSU will implement quality control procedures beginning with the data management system and generate data quality control checks that will be run on the central database. Any missing data or data anomalies will be communicated to the participating clinical study site(s) for clarification and resolution. Monitoring of the day-to-day quality of the trial will be conducted by the Data Manager.

## **14 ETHICS/PROTECTION OF HUMAN SUBJECTS**

### **14.1 Ethical Standard**

The investigators will ensure that this trial is conducted in full conformity with the principles set forth in The Belmont Report: Ethical Principles and Guidelines for the Protection of Human Subjects of Research of the US National Commission for the Protection of Human Subjects of Biomedical and Behavioral Research (April 18, 1979) and codified in 45 CFR Part 46, 21 CFR 50 and 56, and the ICH E6; 62 Federal Regulations 25691 (1997), if applicable. Each investigator's institution will hold a current Federalwide Assurance (FWA) issued by the Office for Human Research Protections (OHRP) for federally funded research.

### **14.2 Institutional Review Board**

An IRB registered with OHRP will review and approve the protocol and informed consent form prior to commencement of subject recruitment at each site.

Prior to enrollment of subjects into this trial, the approved protocol and the informed consent form will be reviewed and approved by the appropriate IRBs listed on their FWA.

The responsible official for the IRB will sign the IRB letter of approval prior to the start of this trial and a copy will be provided to the University of Pittsburgh and DMID. The IRB FWA number will be provided to the University of Pittsburgh and DMID.

All amendments to the protocol or informed consent form will be written by the sponsor, approved before they are placed into use, provided to the investigators for submission to their IRBs, and a copy of the signed IRB letters of approval will be provided to the University of Pittsburgh and DMID.

